**Research Synopsis**

**Study Title:**

Long term outcomes of COVID-19 Critical illness: cohort study of adult patients admitted to the Intensive Care Unit at Mater Dei hospital with COVID-19 infection.

**Study Population:**

All patients admitted to the Intensive Care Unit with organ failure secondary to acute COVID-19 infection and successfully discharged from Mater Dei Hospital and surviving beyond 6 months after discharge, will be offered inclusion in the study.

**Study Design:**

An observational cohort study of patients discharged from the ICU following admission with COVID-19 infection.

**Sample Size:**

From the patients discharged from ITU over the months of September 2020 up until April 2021, we are predicting approximately 100 patients to have survived beyond 6 months after discharge from the unit. These will all be offered inclusion in the study.

**Study Duration:**

May 2021 to May 2022

**Study Agent and Intervention Description (If applicable)**

N/A

**Study Aim:**

To assess the long-term health outcomes of adult patients admitted to Mater Dei Hospital Intensive Care Unit with COVID-19 infection.

**Background and Significance**

The COVID-19 epidemic has placed an unprecedented strain on medical services worldwide. Throughout 2020 and early 2021, hospitals and their critical care services have been inundated with patients suffering from critical illness due to COVID-19, some of whom developed multi-organ failure and required a prolonged ICU stay. While the medical literature is now replete with publications and research on the acute phase of illness due to COVID-19, including critical illness, there is a paucity of studies detailing the long-term outcomes following COVID-19 critical illness.

While the negative long-term physical health, mental health and quality-of-life related effects of ARDS have been well documented, there has been very little long-term COVID-19 ARDS specific outcome studies published.

**Objectives****Primary Objective:**

To assess the long-term health outcomes of adult patients admitted to Mater Dei Hospital Intensive Care Unit with COVID-19 infection.

**Secondary Objectives:**

Specific objective 1:

Observation of the long-term organ failures and medical conditions as a sequela of acute critical illness with COVID-19.

Specific objective 2:

Observation of the effect critical illness due to COVID-19 has on a patients' physical health, mental health and health related quality of life at 6 and 12 months after discharge from the ICU.

Specific objective 3:

Observation of how different severity of critical illness secondary to COVID-19 infection correlates with medium and long-term health related quality of life outcomes.

### **Study design/methodology**

An observational cohort study of patients discharged from the ICU following admission with COVID-19 infection.

All patients discharged from the intensive care unit after a diagnosis of COVID-19 infection will be contacted by phone by one of the members of the research team listed below at six and twelve months after discharge. They will be asked to attend a follow-up appointment at the Pre-Operative Assessment Clinic in Mater Dei Hospital. They will be alone in the room with a researcher to protect their privacy, but they may request to have a person of their choosing such as a relative with them during the interview, if they so wish. For patients unable to attend the hospital appointment, an offer will be extended to perform the interview at their place of residence.

Participants will be asked a number of questions taken from validated questionnaires, namely the Hospital Anxiety and Depression Scale, the Barthel Index and the RAND 36-Item Health Survey. These questionnaires aim to establish the patient's own perception of his or her health, both physical and mental, his or her ability to perform daily activities alone or with help, and the patient's feelings about whether their health has changed since prior to their hospital admission and if so, in what way.

A physical examination will be offered to participants which includes examination of the heart and lungs by auscultation, and recording of height and weight as well as resting blood oxygen saturation via pulse oximetry.

Patients will also be asked to perform a six-minute walk test, if they feel they are able to. This essentially involves walking on a treadmill while clinical non-invasive monitoring such as ECG electrodes, a pulse oximeter and a blood pressure cuff are attached to monitor the vital signs during exercise. The test will be stopped if the patient requests this or if the researcher finds evidence that the patient is unfit to continue the test.

Pulmonary function testing will also be offered. This test would involve breathing through a specialised tube that calculates the flow rates that the patient is able to generate, both during normal breathing as well as during deep breathing. Once again, trained professionals will be performing this test and it will be stopped if the patient requests this or if the health professional deems the patient unfit to proceed with the test.

The participants' medical notes will also be reviewed to obtain retrospective medical history of the patients' initial admission to ICU.

Data collection will take place over a 1-year period between May 2021 and May 2022.

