#### **Analysis Plan:**

Data analysis will initially be quantitative, regarding number of patients surviving beyond 6 months after discharge from ITU following their critical illness with COVID-19. Their residential arrangements following discharge will also be noted (care home or private residence).

Following this initial analysis, results of validated questionnaires which will be used to assess the patients, will be reviewed and this data will be compared to data from other studies regarding the general public of similar age groups as well as persons discharged from ITU after critical illness due to causes other than COVID-19. Their physical assessment (6 minute walk test) and pulmonary function test results will also be analyzed and compared to normal ranges for persons in their age group.

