#### **Special Considerations for Persons who are Unable to Consent:**

In the case of persons who are unable to provide informed consent, the legal carer will be approached for purposes of consent and will be asked to be present with the participant throughout the study session. Questions will be directed at the participant as much as possible but carers will be asked to provide information that participants cannot provide, should they feel comfortable doing so. Participants have a right to refuse to participate in any test or questionnaire that they do not wish to participate in, and carers also have the right to stop patients' participation in any test or questionnaire they feel is inappropriate for the person. In the case that the person regains their capacity to consent for themselves, they will be asked to confirm consent to participate in the study or have their data

removed, although this may not be possible for data that has been included in analysis and publication.

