**Refusal or Withdrawal of Data:**

All participants and their carers are at liberty to refuse to participate in all or part of this research study. Participants and carers may refuse to answer any questions they are uncomfortable with, and may refuse to take any physical test that they do not wish to take. They may also ask to stop their participation in any questionnaire or physical test at any point in time. Participants or their carers may also ask for their data to be deleted after its collection, but should be aware that this may not be possible for data that has already been included in statistical analysis and publication. Refusal to participate in all or part of the study, or withdrawal of data after participation will not result in any loss of benefits and will not incur any penalties or liabilities. Participation is voluntary and any refusal to participate by the patient or guardian will not have any effect on the person's care pathway within the hospital.

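### The walk-test comparison covers only patients who feel able to walk, and the Analysis Plan does not account for tests not done

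*Combined protocol and SAP*

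**What the plan says.** The Study design/methodology section sets out who does the walk test: "Patients will also be asked to perform a six-minute walk test, if they feel they are able to". It adds that "The test will be stopped if the patient requests this or if the researcher finds evidence that the patient is unfit to continue the test". On home visits it says: "For patients unable to attend the hospital appointment, an offer will be extended to perform the interview at their place of residence". No walk test at home is mentioned.

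Refusal is open to everyone. Under Refusal or Withdrawal of Data, participants and carers "may refuse to take any physical test that they do not wish to take". The sections on persons unable to consent and on Data Accessibility say much the same.

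The Analysis Plan starts with the number surviving beyond 6 months and where they live, then turns to the questionnaires. On the physical tests it has one sentence: "Their physical assessment (6 minute walk test) and pulmonary function test results will also be analyzed and compared to normal ranges for persons" of the same age group. It does not name the walk-test measure, the denominator, or what happens to a participant with no result. Nothing elsewhere in the document provides for missing data or for recording why a test was not done.

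Specific objective 2 concerns the effect of the illness on "physical health, mental health and health related quality of life at 6 and 12 months after discharge from the ICU". It is not limited to patients able to walk.

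**The concern.** Most missing-data gaps in a small descriptive cohort are a matter of detail. This one is more specific, because feeling unable to walk is itself a written route to having no walk-test result. Inability to attend hospital may be a second such route. Normal ranges describe people who can do the test. Setting only the performers against them answers a narrower question than objective 2 asks, and probably gives a more favourable picture than the whole assessed group would.

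Refusals unrelated to health also leave gaps, and these need not be linked to function. Unless the reason is recorded at the visit, the two kinds of gap are hard to tell apart afterwards. There are two visits, and a patient may be tested at one and not the other. An apparent change from 6 to 12 months could then partly reflect who was tested.

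**Working it through.** **1. What can be reproduced.** Nothing numerical. The plan gives no non-completion rate, expected distance or target precision. Its only count is approximately 100 survivors, of whom it says "These will all be offered inclusion in the study". That is the number invited, not the number assessed or tested.

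**2. Routes to having no result.**

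| Route in the plan | Linked to walking ability? | Handling in the Analysis Plan |
|---|---|---|
| Patient does not feel able | Yes, directly | None stated |
| Seen at home, interview only mentioned | Possibly; could also be logistics | None stated |
| Patient or carer refuses | Not necessarily | None stated |

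**3. General result.** Let u be the share of assessed participants without a walk-test result, q the proportion below normal among performers, and r the proportion impaired among the untested.

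- Proportion impaired in the cohort = (1−u)q + ur.
- Performers minus cohort = q − [(1−u)q + ur] = u(q − r).

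The performers-only figure is right if r = q, too low if r > q and too high if r < q. With r unknown, the cohort proportion lies between (1−u)q and (1−u)q + u, a range of width u.

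Now let h be the share of the untested who could not do the test for health reasons, and count them as impaired. If reasons are recorded, the range becomes uh + (1−u)q to u + (1−u)q, of width u(1−h).

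**4. Illustration.** Every input is an assumption: q = 40%, h = 50%.

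| u | Performers only | Reason not recorded | Reason recorded |
|---|---|---|---|
| 10% | 40% | 36–46% | 41–46% |
| 20% | 40% | 32–52% | 42–52% |
| 30% | 40% | 28–58% | 43–58% |

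The 20% row in counts, for 100 assessed: 80 perform the test, and 0.40 × 80 = 32 are below normal. Of the 20 untested, 10 are unable for health reasons and 10 are missing for other reasons. Reason not recorded: 32/100 to (32 + 20)/100. Reason recorded: (32 + 10)/100 to (32 + 20)/100.

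**5. How far the inputs drive the answer.** The lower limit with reasons recorded exceeds q exactly when uh + (1−u)q > q, that is, when h > q. The right-hand column lies above 40% only because h was set at 50%. At u = 20%:

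- q = 40%, h = 25%: 0.05 + 0.32 = 37%, up to 52%. This includes 40%.
- q = 40%, h = 75%: 0.15 + 0.32 = 47%, up to 52%.
- q = 30%, h = 50%: 0.10 + 0.24 = 34%, up to 44%.
- q = 50%, h = 50%: 0.10 + 0.40 = 50%, up to 60%. The lower limit equals q.

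The halving of the range in step 4 is likewise just 1 − h with h = 50%.

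**6. Against sampling error.** The 95% half-width is 1.96 × √(0.4 × 0.6/n). With 20% untested and 100, 75 or 50 assessed, n is 80, 60 or 40, and the half-width is 10.7, 12.4 or 15.2 points. At 100 assessed, the 20-point range from untested patients is about as wide as the sampling interval (2 × 10.7 = 21.4 points).

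**The case against.** The strongest reply is that nothing in the Analysis Plan commits the investigators to a misleading statement. Results could be reported as so many below normal out of so many tested, which is accurate for those tested. Harm needs two further conditions: non-performers go unreported, and they are more impaired than performers. The illustration does not establish the second, since its direction follows from the choice of h and q. This stands, and it is why the conclusion is conditional.

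It is also fair to say that the study is descriptive, that the walk test is not named as primary, and that objective 2 draws on the RAND 36-Item Health Survey, the Barthel Index and a physical examination as well. These would give some indication of whether a non-performer was limited, so it would be too strong to say that the reasons could never be reconstructed. The help is only partial. Questionnaires can be declined too. The provision that "carers will be asked to provide information that participants cannot provide, should they feel comfortable doing so" applies only to persons unable to consent. None of these measures records why the walk test was not done. The opening count of survivors in the Analysis Plan gives an outer total, but not the number assessed or tested.

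The data form is not among the documents. Their silence shows that recording a reason is unspecified, not that it will not happen.

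Finally, a voluntary test is proper for safety and consent. The point concerns recording and analysis only.

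**Conclusion.** The gap is real and should be closed, though it does not undermine the study as a whole. The plan makes having a walk-test result depend partly on the function being tested, and then compares results with norms without accounting for tests not done. On available results the comparison applies to performers only. It is likely to understate impairment in the cohort of objective 2, on the assumption that untested patients are impaired more often than tested ones. There is no bias if the two are impaired equally often. The size cannot be derived; the percentages shown are illustrations, not estimates for this study.

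Three stronger readings are tempting and not supported:

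- A reader might infer that understatement is demonstrated. It is not. Refusal for any reason is allowed, and with a quarter of non-performance health-related the illustrative range includes the performers' figure.
- A reader might infer that tests stopped early also bias the result. None is shown. If distance is the measure, a shortened walk may still be counted as below normal.
- A reader might infer that the same holds for lung function. That testing is offered and can be refused or stopped, but it is not conditioned on perceived ability, and the direction of any error is uncertain.

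**What to change.** At each visit, record the walk test as done, stopped early or not done, with the reason: health-related, refusal unrelated to health, or logistics. A patient seen at home counts as unable only if the recorded reason is health-related.

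In the Analysis Plan, name the walk-test measure and state that the following will be reported at 6 and at 12 months, over all participants assessed at that visit, including at home:

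1. The numbers done, stopped early and not done, by reason.
2. As the cohort-level result, the proportion unable for health reasons or below normal.
3. Tests stopped early for health reasons, shown as a subgroup and classified by the distance reached. If a measure other than distance is named, the plan must say how a stopped test is classified on it.
4. Tests not done or stopped for any other reason, treated as missing, with best-case and worst-case bounds on the proportion in item 2.
5. The comparison of performers with normal ranges, kept and labelled as applying to performers only.

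For lung function, report counts by status and reason only, and do not recode untested patients as abnormal. Testing, refusal and stopping rules stay unchanged.

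The cost is one status-and-reason code per test, one extra table per visit and some added text in the Analysis Plan. Someone must judge whether non-performance was health-related, and the reason is captured reliably only at the visit. The result may look less favourable, with wider stated uncertainty.

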### **Study Population**

All patients admitted to the Intensive Care Unit with organ failure secondary to acute COVID-19 infection and successfully discharged from Mater Dei Hospital and surviving beyond 6 months after discharge, will be offered inclusion in the study.

#### **Inclusion /Exclusion Criteria:**

A positive COVID PCR result before or during the patient's admission will be necessary for inclusion in the study. Participants will be over 18 years of age, with no restriction as regards race, ethnicity or gender.

#### **Study Schedule:**

Enrollment of participants and initiation of data collection is projected to start in May 2021. Participants will initially be included after 6 months from discharge from ITU, at which point they will be invited to attend for an interview, physical examination and pulmonary function tests. This will be repeated 12 months after discharge from ITU.

Data collection will take place over a 1-year period between May 2021 and May 2022. This will be followed by a period of data analysis with completion of the study by the end of 2022.

#### **Analysis Plan:**

Data analysis will initially be quantitative, regarding number of patients surviving beyond 6 months after discharge from ITU following their critical illness with COVID-19. Their residential arrangements following discharge will also be noted (care home or private residence).

Following this initial analysis, results of validated questionnaires which will be used to assess the patients, will be reviewed and this data will be compared to data from other studies regarding the general public of similar age groups as well as persons discharged from ITU after critical illness due to causes other than COVID-19. Their physical assessment (6 minute walk test) and pulmonary function test results will also be analyzed and compared to normal ranges for persons in their age group.

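### Walk and lung function results are compared with normal ranges for which only age group is named; sex and height should enter the lung function comparison through a named reference equation

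*Combined protocol and SAP*

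**What the plan says.** The Analysis Plan deals with both physical tests in one sentence. It begins "Their physical assessment (6 minute walk test) and" and ends "pulmonary function test results will also be analyzed and compared to normal ranges for persons in their age group". Age group is the only matching variable. Neither this section nor any other names a reference equation, an adjustment for sex or body size, percent predicted, a z-score, a lower limit of normal or a rule for calling a result abnormal.

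Three other places bear on the point.

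- The Inclusion/Exclusion Criteria admit both sexes: "Participants will be over 18 years of age, with no restriction as regards race, ethnicity or gender". The expected proportion of men is not stated.
- Study design/methodology plans the body size measurements: "A physical examination will be offered to participants which includes examination of the heart and lungs by auscultation, and recording of height and weight". They are given no role in the analysis. The same section plans a review of the medical notes and says of the walk test: "This essentially involves walking on a treadmill".
- The Study Schedule has the assessments at 6 months and adds "This will be repeated 12 months after discharge from ITU", so each patient may have two results.

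**The concern.** This is a single cohort without a control group. For the walk and lung function, the external normal range is the only stated comparison with normal. (The questionnaires have their own comparison with the general public and with other ICU survivors.)

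If lung function depends on sex and height as well as age, a range specific to age alone averages over people with different expected values. A healthy tall man then looks better than normal and a healthy short woman looks worse. At group level, a difference from the range mean mixes loss due to disease with a difference in sex mix between cohort and reference population. As the plan states neither mix, a reader could not separate the two.

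**Working it through.** **What can be checked from the documents.** There is no figure to reproduce: the plan gives no predicted value, limit, standard deviation or sex mix. The textual check is simple. One sentence names age, two other sections show that both sexes are eligible and that height is measured, and nothing connects them.

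**Illustration, lung function only, at a fixed age.** All inputs are assumptions:

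- male-female height gap 10, 13 or 15 cm, centred on 168.5 cm;
- height SD within sex 6, 7 or 8 cm;
- lung function proportional to height to the power 1.8, 2.15 or 2.5;
- further male effect 0, 5, 10 or 15%;
- residual coefficient of variation 10, 13 or 16%, normal or log-normal;
- cohort and reference each 50% or 70% men.

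**Step 1: group mean of a healthy cohort.** Let R be the ratio of the male to the female mean, p_c the proportion of men in the cohort and p_r that in the reference. Then

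cohort mean / range mean = (p_c R + 1 − p_c) / (p_r R + 1 − p_r).

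Middle case, evaluated at the mean heights (175 and 162 cm, power 2.15, male effect 10%): R = (175/162)^2.15 × 1.10 = 1.299.

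- Cohort 70% men, reference 50%: (0.7 × 1.299 + 0.3) / (0.5 × 1.299 + 0.5) = 1.209/1.149 = 105%.
- Reverse: 1.149/1.209 = 95%.

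The ends of the range:

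| Height gap, power, male effect | R | 70% men vs reference 50% | 50% men vs reference 70% |
|---|---|---|---|
| 10 cm, 1.8, 0% | (173.5/163.5)^1.8 = 1.113 | 102% | 98% |
| 15 cm, 2.5, 15% | (176/161)^2.5 × 1.15 = 1.437 | 107% | 93% |

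Integrating over the height distribution gives the same rounded ranges: 102-107% and 93-98%. If p_c = p_r the ratio is 1 whatever R is.

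**Step 2: individual classification.** This needs a rule that the plan does not state. Suppose a limit at the 5th percentile of the reference, pooled over sex and height. Over all combinations of the inputs above, by numerical integration over height, 0-3.3% of healthy men and 7-17% of healthy women fall below it, instead of 5% each.

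A simpler model gives the same direction. Take two normal distributions with SD 1, means d apart, and a 50:50 reference. The limit c solves 0.5 Φ(c − d/2) + 0.5 Φ(c + d/2) = 0.05. For d = 1, c = −1.84, so Φ(−2.34) = 1.0% of men and Φ(−1.34) = 9.0% of women are flagged. For d = 0.5 the figures are 2.6% and 7.4%; for d = 2 they are 0.1% and 9.9%.

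**Step 3: is sex alone enough?** Take a male-only range that ignores height, mean 175 cm, with the same ranges for the other inputs. A healthy man 10 cm above the mean is flagged 0-1.6% of the time, and one 10 cm below 10-24%. Height is therefore needed too.

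**Step 4: overall direction.** Compare the pooled limit with a limit specific to sex and height, at uniform losses of 0, 5, 10, 20 and 30%. In these scenarios the pooled limit flags more patients overall only where the cohort has fewer men than the reference (50% against 70%), and even there not at a 30% loss.

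**The case against.** The strongest reply is that this is a short sentence in a short protocol, not a complete list of covariates. A range matched on age may also be matched on sex and height. Trained professionals perform the lung function test, and the testing service may supply predicted values that already use both; the documents do not say. This stands. A reader might infer that the plan commits to age-only ranges and so contains an analysis error. The text does not support that: it leaves the matter open.

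Second, the figures rest on assumptions. Every scenario makes men taller and sets the male effect at zero or above, so the sex direction follows from the inputs. The 5th-percentile results also need a classification rule that the plan lacks. Both points stand; only the group mean comparison needs no added rule, and it shows no bias when the sex mixes match.

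Third, nothing has been calculated for the walk. It would be tempting to carry the lung function direction over to it, but the documents give no basis for doing so.

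Fourth, within-patient change gives a second yardstick. The Secondary Objectives cover "physical health, mental health and health related quality of life at 6 and 12 months after discharge from the ICU", and the range largely cancels in a patient's ratio of 12-month to 6-month result. This is true, but such a ratio does not show whether the patient is normal, which is the question that the Analysis Plan sets for these tests.

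What survives is that the plan does state a comparator, names one variable for it, and leaves out two that it could use at almost no cost.

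**Conclusion.** The point holds as a cheap improvement, mainly for lung function. The plan names age only. Followed as written in a cohort of both sexes, it would set the range too low for men and tall patients and too high for women and short patients, and would tie the group result to the sex mix.

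Under the assumed inputs the shift in a healthy group mean is about 2 to 7% in either direction when the mixes are 70% and 50% men, and nil when they match. Actual mixes are not stated, so neither the size nor the sign is known for this cohort. A reader might conclude that the study will overstate, or understate, impairment overall. Neither follows, because the net direction depends on the cohort's sex mix relative to the reference and on the size of the true loss. No sample size or error rate in the plan is affected.

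**What to change.** In the Analysis Plan:

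1. **Lung function.** Replace the age-group range with percent predicted or z-score from one pre-specified reference equation using age, sex and height. If results are classified, use the individual lower limit of normal from that equation.
2. **Walk test.** Use a pre-specified equation that includes sex and body size where one suits the test as performed. State any mismatch with the treadmill mode as a limitation.
3. **Data.** Take sex from the planned notes review, and report how many patients lack height or weight.

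The cost is a few sentences and slightly more analysis work; no visit or test is added. The drawback is missing data. The examination is only offered, and participants "may refuse to take any physical test that they do not wish to take", so those who decline it will have no predicted value. The documents give no basis for estimating how many. A reference equation that suits a treadmill walk may not exist, in which case the stated limitation has to serve.
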